2.2.2 Clinical Data to Date

In Phase 3 clinical trials, 8 weeks of Mavyret therapy achieved high rates (98%) of SVR across all genotypes (1-6) of HCV in patients with HCV infection without cirrhosis. Clinical trials involved over 2300 patients in 27 countries. Based on the results of clinical trials, the FDA approved Mavyret for use in the treatment of HCV (all strains) in patients without cirrhosis. (ClinicalTrials.gov identifiers:

NCT02651194, NCT02642432, NCT02640482, NCT02636595, NCT02604017, NCT02446717, NCT02640157, NCT02243293) [9-14].

Included in the clinical trial populations were patients with severe renal impairment (stage 4 or 5 CKD). In this population Mavyret was found to be effective in achieving a high rate of SVR and no dosing adjustment was required [15].

CONFIDENTIAL

This material is the property of the NYU School of Medicine and Langone Medical Center. Do not disclose or use except as authorized in writing by the study sponsor
Interventional Template Version: 28 APR 2017

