2.4 Potential Risks & Benefits

2.4.1 Known Potential Risks

Risks of treatment failure: HCV mutation can lead to drug resistance and treatment failure. In patients administered Mavyret, the risk of this was 2% or less. For patients with treatment resistant HCV, rescue therapy with alternative agents can result in cure of up to 100% depending upon the genotype. Guidelines for the treatment of resistant HCV strains are published and updated regularly [16].

Risks of treatment intolerance: Over multiple clinical trials, the overall rate of medication related adverse events leading to permanent discontinuation prior to completion of an 8-week course of Mavyret therapy was 0.1% [17].

Risk of acute hepatitis C infection: Acute hepatitis C is asymptomatic in 66-75% of patients. The risks of acute HCV leading to fulminant hepatic failure are believed to be very low, however case reports of this do exist [18]. During the time that patients are acutely infected with hepatitis C infection, it is possible that patients could transmit infection to other individuals, if others individuals are exposed to the patient's blood. Family members who, for instance, assist patients with medical care such as diabetic blood sugar monitoring, could potentially be exposed to hepatitis C if they were to sustain a needlestick injury from a needle used by the patient. The risk of an infected individual transmitting hepatitis C via a needlestick exposure is approximately 5%. Patients in the study will be counseled to use caution to prevent blood exposure to other individuals and will be asked to notify the study team immediately if they believe any individuals were exposed to their blood during the duration of the study participation.

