10.4 Description of Statistical Methods

Since the anticipated study population will be a small size, statistical analyses will be limited to descriptive statistics. For patients who develop post-transplant viremia we will be able to compare our HCV cure rates to those that are expected for patients who receive treatment with these agents for chronic HCV.

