10.4.1 General Approach

The study design will be single arm, open label. Descriptive statistics will include:

Incidence HCV viremia post-transplant (percentage)

Time course of exposure to development of clinically detectable viremia in those who develop viremia (median time to viremia with standard deviations)

Incidence of sustained clearance of HCV (cure) after treatment of viremia (percentage)

Time course of clearance of viremia after treatment initiation (median time to clearance with standard deviations)

Incidence of treatment failure/treatment resistant strains of HCV (percentage)

Characterization of distribution of HCV genotypes in patients who develop viremia (percentages)

Comparison of treatment failure rates to expected treatment failure rates for the treatments used (p value for significance will be set at $p < 0.05$ and two-tailed t-test will be used)

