10.5 Sample Size

10 patients are expected to enroll in this trial.

We expect that less approximately 70% of patients will develop evidence of HCV infection transmitted from the HCV-positive donor and will be treated for HCV infection. We expect that 100% of the patients who are treated for HCV infection will achieve SVR.

This is a single-arm study with no comparison group. The power to detect a difference in observed versus expected depends upon the true efficacy of the therapy. The reported efficacy of the therapy is 98%. With an estimated 7 patients who will be treated, a single treatment failure will be regarded as a significant deviation from the expected outcome.

11 Source Documents and Access to Source Data/Documents

Source data is all information, original records of clinical findings, observations, or other activities in a clinical trial necessary for the reconstruction and evaluation of the trial. Source data are contained in source documents. Examples of these original documents, and data records include: hospital records, clinical and office charts, laboratory notes, memoranda, subjects' diaries or evaluation checklists, pharmacy dispensing records, recorded data from automated instruments, copies or transcriptions certified after verification as being accurate and complete, microfiches, photographic negatives, microfilm or magnetic media, x-rays, subject files, and records kept at the pharmacy, at the laboratories, and at medico-technical departments involved in the clinical trial. It is acceptable to use CRFs as source documents. If this is the case, it should be stated in this section what data will be collected on CRFs and what data will be collected from other sources.

The study case report form (CRF) is the primary data collection instrument for the study. All data requested on the CRF must be recorded. All missing data must be explained. If a space on the CRF is left blank because the procedure was not done or the question was not asked, write "N/D". If the item is not applicable to the individual case, write "N/A". All entries should be printed legibly in black ink. If any entry error has been made, to correct such an error, draw a single straight line through the incorrect entry and enter the correct data above it. All such changes must be initialed and dated. DO NOT ERASE OR WHITE OUT ERRORS. For clarification of illegible or uncertain entries, print the clarification above the item, then initial and date it.

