#### 1.4.1 General Approach

The study design will be single arm, open label. Descriptive statistics will include:  
Incidence HCV viremia post-transplant (percentage)  
Time course of exposure to development of clinically detectable viremia in those who develop viremia (median time to viremia with standard deviations)  
Incidence of sustained clearance of HCV (cure) after treatment of viremia (percentage)  
Time course of clearance of viremia after treatment initiation (median time to clearance with standard deviations)  
Incidence of treatment failure/treatment resistant strains of HCV (percentage)  
Characterization of distribution of HCV genotypes in patients who develop viremia (percentages)  
Comparison of treatment failure rates to expected treatment failure rates for the treatments used (p value for significance will be set at  $p < 0.05$  and two-tailed t-test will be used)

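### A two-tailed t-test is unsuitable for a yes/no failure rate in about 7 patients, and section 10.5 calls one failure a significant deviation although at least one is 13% likely at 98% efficacy

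*Protocol*

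**What the plan says.** Protocol 10.4 states that "statistical analyses will be limited to descriptive statistics", and SAP 1.4 says the same. The list of descriptive statistics in Protocol 10.4.1, repeated in SAP 1.4.1, nevertheless ends with a significance test: "Comparison of treatment failure rates to expected treatment failure rates for the treatments used", at p<0.05, "and two-tailed t-test will be used". Neither document says whether the test is one-sample or two-sample, and neither gives the expected rate at that point.

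The other inputs are in Protocol 10.5: about 70% of 10 patients will be treated, 100% of them are expected to reach sustained virologic response (SVR), reported efficacy is 98%, and there is no comparison group. On sensitivity it says that "The power to detect a difference in observed versus expected depends upon the true efficacy of the therapy", gives the 98% figure, and continues: "With an estimated 7 patients who will be treated, a single treatment failure will be regarded as a significant deviation from the expected outcome".

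Protocol 5.4 and 5.6 give 20 patients rather than 10, so the check below also covers 14 treated.

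**The concern.** SVR is presence or absence of detectable virus, so each treated patient contributes a 0 or a 1. A t-test takes its standard error from the observed spread of those values. When nobody fails the spread is zero, and no failures is what the protocol expects. When one or two fail in 7, the estimated standard error is large and the test has little power.

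The form of the test also matters and is left open, so it could be chosen after the data are seen. Section 10.5 meanwhile attaches the word significant to a result that may not meet the plan's own threshold.

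This is the only significance test in the plan, and it bears on the cure rate, which is the primary endpoint. The harm would be a wrong or arbitrary statement in the report on whether donor-derived infection is cured as often as expected.

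**Working it through.** **Inputs.** Expected failure rate 2%, from 98% efficacy (10.5); section 2.4.1 agrees: "In patients administered Mavyret, the risk of this was 2% or less". Two-sided alpha 0.05 (10.4.1). Number treated: 10 × 0.70 = 7, which reproduces the plan's figure, or 20 × 0.70 = 14 with the enrolment in 5.6.

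**One-sample t-test against 0.02, n = 7.** t = (k/7 − 0.02)/(s/√7), where k is the number of failures and s the sample SD of the 0/1 values. For k = 1, s/√7 = 0.1429 and t = 0.1229/0.1429 = 0.86 on 6 df. The exact column is the two-sided binomial p-value, the summed probability of all outcomes no more likely than the one observed.

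| Failures of 7 | t | p, one-sample t | p, exact binomial |
|---|---|---|---|
| 0 | undefined (s = 0) | none | 1.00 |
| 1 | 0.86 | 0.42 | 0.132 |
| 2 | 1.44 | 0.20 | 0.0079 |
| 3 | 2.02 | 0.090 | 0.0003 |
| 4 | 2.73 | 0.034 | <0.0001 |

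The undefined row has probability 0.98^7 = 0.868 at a 2% failure rate. Software may return t = −∞ and p = 0 there, which is spurious. With 14 treated, the t-test gives p=0.054 at 4 failures and 0.025 at 5.

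**Error and power of the one-sample form.** If the undefined case counts as no rejection, the type I error at 2% is P(X ≥ 4) = 0.000005, so the test is degenerate and weak, not liberal. The exact test rejects at 2 or more.

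| True failure rate, n = 7 | Power, one-sample t: P(X ≥ 4) | Power, exact: P(X ≥ 2) |
|---|---|---|
| 10% | 0.3% | 15.0% |
| 20% | 3.3% | 42.3% |
| 30% | 12.6% | 67.1% |

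These true rates are illustrative; the protocol gives no alternative.

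**Two-sample forms.** Assumption: 2300 historical patients with 2% failures, that is 46. The size is taken from section 2.2.2 ("Clinical trials involved over 2300 patients in 27 countries"); the count is assumed.

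- Pooled: 0 of 7 gives p=0.71; 1 of 7 gives t = 2.30, p=0.022.
- Welch: 0 of 7 gives t = −6.85, p<0.0001, so a perfect cure rate would be declared significantly different; 1 of 7 gives p=0.42.

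**The single-failure statement in 10.5.** P(at least 1 failure) = 1 − (1 − failure rate)^n.

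| Failure rate | n = 7 | n = 14 |
|---|---|---|
| 2% | 13.2% | 24.6% |
| 1% | 6.8% | 13.1% |
| 0.5% | 3.4% | 6.8% |

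Exactly one failure of 7 at 2% has probability 7 × 0.02 × 0.98^6 = 12.4%. For one failure to meet p<0.05, the reference failure rate must be no more than 1 − 0.95^(1/7) = 0.73% (efficacy 99.3%) with 7 treated, or 1 − 0.95^(1/14) = 0.37% (efficacy 99.6%) with 14. At 2%, one failure is significant only if 1 or 2 patients are treated; with 3 the p-value is already 0.059.

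**Exact results across plausible n.** Two failures give p=0.008 at n = 7, 0.031 at n = 14, 0.0495 at n = 18 and 0.055 at n = 19. Clopper-Pearson 95% intervals for the failure rate: 0/7, 0 to 41%; 1/7, 0.4 to 58%; 0/14, 0 to 23%; 1/14, 0.2 to 34%; 2/14, 1.8 to 43%.

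**The case against.** **Section 10.5 may use significant in a clinical sense.** It does not say statistically. Sections 10.2, 10.4.2 and 10.5 all expect 100% SVR, and against an expectation of no failures any failure is a deviation. Section 8.6 also calls an emergency safety-board meeting for any treatment failure. This reading is possible. However, the sentence directly follows the statement on power and the 98% figure, and 10.4.1 ties significance to p<0.05. If a clinical meaning is intended, the text should say so. The t-test problem stands either way.

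**The two-sample figures are a construction.** No section says that historical patient data will be used, and 2300 is not stated to be the denominator of the 98%. They show only that another form of t-test would not rescue the plan. The one-sample results do not depend on them.

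**With 7 patients no test has much power.** This is right: at a true 10% failure rate the exact test has 15.0% power. It still does better than the t-test at each rate examined and can be computed at every outcome.

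**Little depends on the test.** The primary analysis is a percentage, and no stopping or success rule uses the p-value. That limits the harm to the reported conclusion. Deleting the test and reporting the proportion with an exact interval would also remove the fault, and would agree with 10.4. The 10.5 sentence would still need rewording.

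**Conclusion.** The concern holds. The prescribed t-test is the wrong method for this outcome and sample size. On the one-sample reading it has no value in the most likely case (87% at 2% failure) and needs 4 failures of 7, or 5 of 14, to reject. The same observation of 1 in 7 gives p=0.42 or p=0.022 according to a choice the plan leaves open, the second figure resting on the assumed 46/2300.

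Taken against 98% efficacy, the statement in 10.5 does not meet the plan's own threshold: at least one failure is 13.2% likely with 7 treated and 24.6% with 14. It would hold with 7 treated only against a reference efficacy of at least 99.3%.

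This should be fixed before analysis, but it does not threaten the conduct of the study.

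**What to change.** - **Protocol 10.4.1 and SAP 1.4.1:** replace the t-test with a two-sided exact binomial test of the failure rate against 2%, computed at the actual number treated. Report the failure (or SVR) proportion with its Clopper-Pearson 95% interval.
- **Protocol 10.4 and SAP 1.4:** name this test as the one exception to the restriction to descriptive statistics.
- **Protocol 10.5:** replace the single-failure sentence with, for example: *One failure is compatible with 98% efficacy (exact p=0.13 if 7 are treated, 0.25 if 14); two or more would be a significant deviation (p=0.008 if 7, 0.031 if 14).* Two failures suffice up to 18 treated. At 70% transmission in 20 patients, 19 or more treated has probability 20 × 0.7^19 × 0.3 + 0.7^20 = 0.8%.
- **Criterion:** state that the p-value decides, not the interval. The two can disagree: at 2 of 14, p=0.031 but the lower limit is 1.8%, below 2%.
- **Protocol 8.6:** leave the emergency review of any treatment failure as it is, as a separate safety action.

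The cost is wording in the protocol and SAP. The stated sensitivity to a single failure becomes less favourable.

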10.4.2 Analysis of the Primary Efficacy Endpoint(s)

The primary endpoint will be percentage of patients with sustained virologic response after treatment for HCV after heart transplant.

We expect that 100% of patients who are treated will achieve SVR. SVR will be defined as the absence of detectable HCV by NAT testing 3 months after the completion of the treatment course.

10.4.3 Analysis of the Secondary Endpoint(s)

Secondary endpoint #1: 1-year patient survival rates in HCV negative heart recipients who receive a heart transplant from a HCV positive donor.

CONFIDENTIAL

This material is the property of the NYU School of Medicine and Langone Medical Center. Do not disclose or use except as authorized in writing by the study sponsor

Patients will have regular follow-up as standard of care for all heart transplant recipients. Patients survival will be readily apparent. Furthermore, all deaths of transplant recipients are required to be reported to UNOS.

Secondary endpoint #2: Incidence of HCV viremia among HCV negative recipients who receive a heart transplant from a HCV positive donor.

We will be measuring serial HCV NAT and serologic testing for a minimum of 6-months post-transplant. A patient will be considered to be viremic when a post-transplant HCV NAT test is positive. The incidence of viremia will be calculated as a percentage of the patients transplanted with a HCV-positive donor who develop HCV viremia by NAT testing.

10.4.4 Safety Analyses

Safety concerns will be evaluated in real time. All AEs deemed to be related to the drug Mavyret will be evaluated by the PI. Any SAE deemed related to the drug Mavyret will be reported to the Monitoring committee within 3 days of PI notification of the event. Any AE or SAE deemed related to acute HCV infection will be reported to the Monitoring committee within 3 days of its determination. Any patient who is deemed a treatment failure (as defined by persistence of HCV viremia after completion of the full course of therapy) will be reported to the DSMB and the IRB within 3 days of its determination. A rescue course of therapy will be initiated under the direct guidance of a hepatologist and/or transplant infectious diseases specialist.

10.4.5 Adherence and Retention Analyses

Adherence to the protocol will be assessed by the study team in direct conversations with the patients during routing visits, and will be assessed clinically by evaluation of HCV viral loads. Clearance of HCV will demonstrate adherence to the regimen. Failure to clear viremia will prompt more detailed direct patient inquiries regarding and will prompt an evaluation of possible treatment resistant strains of HCV as described elsewhere.

10.4.6 Baseline Descriptive Statistics

In this study, no designed comparison groups will exist. The “No Transmission” arm and the “Mavyret treatment” arm will not be comparable groups with regard to the outcomes of this study.

10.4.7 Planned Interim Analysis

Interim analysis not applicable

10.4.7.1 Safety Review

Any patient death will result in halting of any further enrollment in the study and an assessment of whether the death was related to HCV exposure, infection, or treatment. Even in the event of a patient death, currently enrolled patients who are actively being treated for HCV viremia and tolerating therapy will continue to receive therapy so as not to put them at risk for HCV infection and/or the development of resistance as a consequence of interrupted therapy. If the patient death is deemed related to a specific treatment agent, enrolled patients receiving that same agent will be switched to an alternative therapy.

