7.6 Rescue Medications, Treatments, and Procedures

In the event that a subject fails to achieve SVR with Mavyret, rescue therapy with other marketed agents approved for the treatment of HCV will be administered. The rescue treatment will be determined based on genotyping and resistance testing, and the choice of drug(s) used will be prescribed under the direction of a transplant hepatologist and/or transplant infectious diseases physician.

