8.5 Study Halting Rules

Further enrollment of study subjects will be halted under the following conditions:

- Any patient death occurs and is deemed related to the intervention
- Any SAE deemed related to acute HCV infection occurs
- Any SAE deemed related to Mavyret occurs

The PI will inform the IRB and the DSMB within 24 hours of any of these events. The DSMB and study team will convene an emergency meeting as described below. The DSMB will provide recommendations for proceeding with any further enrollment. Patients who are already enrolled and receiving Mavyret treatment will continue to receive treatment unless the DSMB determines that an alternate course of therapy should be pursued for already-enrolled subjects.

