8.6 Safety Oversight

It is the responsibility of the Principal Investigator to oversee the safety of the study. This safety monitoring will include careful assessment and appropriate reporting of adverse events as noted above, as well as the construction and implementation of a site data and safety-monitoring plan. Medical monitoring will include a regular assessment of the number and type of serious adverse events.

Safety oversight will be under the direction of a DSMB. This DSMB committee for this study will be comprised of individuals with expertise in transplantation, hepatology, infectious diseases and the treatment of hepatitis C, and ethics. These individuals will be:

[name] – Expert in medical ethics

[name] – Transplant nephrologist

[name] – Cardiologist

[name] – Cardiologist

[name] – Hepatologist

[name] – Transplant infectious diseases

The DSMB Charter with specific outlines of DSMB roles and responsibilities is uploaded as a separate attachment in Research Navigator.

The DSMB will be notified of all AEs and SAEs as outlined above in 8.4.1 and 8.4.2. Regular meetings of the DSMB and the study team will occur on a quarterly basis to review non-emergent AEs and SAEs.

The minimum group required to constitute an adequate DSMB-study team meeting will be (either in person or by teleconference): at least 4 of the DSMB members listed above, the PI, and at least one co-investigator. At quarterly meetings the DSMB will evaluate cumulative participant safety data and make recommendations regarding the safe continuation of the study.

The DSMB and study team will meet on an emergency basis in the following instances:

- Any SAE occurs that is unexpected and deemed related to the study intervention
- Any unanticipated problem occurs that is both serious and deemed related to the study intervention
- Any treatment failure occurs or drug resistant HCV strain is identified, and a rescue plan with alternate therapy is required

Emergency meetings will occur within one business day of the above-described event occurring or being recognized. Any event that prompts an emergency DSMB-study team meeting will be reported to the IRB within 24 hours of the event occurring or being recognized.

9 Clinical Monitoring

CONFIDENTIAL

This material is the property of the NYU School of Medicine and Langone Medical Center. Do not disclose or use except as authorized in writing by the study sponsor
Interventional Template Version: 28 APR 2017

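### The protocol gives conflicting safety rules on whether an unrelated death halts enrolment, how fast the IRB must be told of certain events, and whether an unexpected related SAE requires an emergency meeting

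*Protocol*

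**What the plan says.** **Death.** Protocol 8.5 halts further enrolment under three listed conditions. The one for deaths reads: "Any patient death occurs and is deemed related to the intervention". Protocol 10.4.7.1 reads: "Any patient death will result in halting of any further enrollment in the study", and makes the assessment of relatedness part of the response to the death.

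**Treatment failure.** Protocol 8.6 lists this among the events that require an emergency meeting of the DSMB and study team: "Any treatment failure occurs or drug resistant HCV strain is identified, and a rescue plan with alternate therapy is required". It adds: "Emergency meetings will occur within one business day of the above-described event occurring or being recognized". Any event that prompts such a meeting "will be reported to the IRB within 24 hours of the event occurring or being recognized". Protocol 10.4.4 says that a treatment failure "will be reported to the DSMB and the IRB within 3 days of its determination".

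**Unanticipated problems.** Protocol 8.4.3 gives 3 days for notifying the IRB, with a separate line giving the same limit for those that are SAEs. Protocol 8.6 puts those that are serious and judged related on the emergency list, so its 24-hour IRB limit applies to them.

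**Unexpected related SAEs.** Protocol 8.6 puts these on the emergency list as well. Protocol 8.4.2 requires notice to the IRB and DSMB within 24 hours, then leaves the DSMB to decide between an emergency meeting and quarterly review.

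The SAP text contains no safety rules and settles none of these points.

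**The concern.** The study deliberately exposes uninfected recipients to HCV. These rules decide when enrolment stops, when the DSMB meets and when the IRB is told. If one event has two rules, staff who follow one section can breach another, and neither the DSMB nor the IRB can audit compliance.

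The death rule matters in both directions. The protocol justifies the study by waiting-list mortality (2.3, 2.4.1), so an unintended halt has a cost to candidates, and so does an unintended continuation.

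Treatment failure is also central to the trial. Protocol 10.5 says that a single failure among an estimated 7 treated patients will be regarded as a significant deviation from expectation.

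**Working it through.** The plan states no figure for these rules, so there is nothing to reproduce. The check sets the sections side by side.

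| Event | One rule | Other rule | Where they conflict |
|---|---|---|---|
| Death | 8.5: halt if judged related | 10.4.7.1: halt for every death, then assess | Deaths not judged related |
| Treatment failure needing rescue | 8.6: IRB within 24 hours, meeting within one business day | 10.4.4: DSMB and IRB within 3 days | Every failure under 10.4.4 (step 2) |
| Unanticipated problem | 8.6: IRB within 24 hours if serious and judged related | 8.4.3: IRB within 3 days | The serious, related subset only |
| Unexpected related SAE | 8.6: emergency meeting mandatory | 8.4.2: DSMB may leave it to a quarterly meeting | All such SAEs |

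**Step 1, death.** For a related death the two sections agree. They differ only for an unrelated one. If 10.4.7.1 governs, the relatedness condition in 8.5 does no work. If 8.5 governs, the halt in 10.4.7.1 is too wide.

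**Step 2, do 8.6 and 10.4.4 cover the same failures?** The 8.6 trigger requires that rescue be needed. Protocol 10.4.4 says of treatment failures: "A rescue course of therapy will be initiated under the direct guidance of a hepatologist and/or transplant infectious diseases specialist". Protocol 7.6 says that for a subject who does not reach SVR, "rescue therapy with other marketed agents approved for the treatment of HCV will be administered". Every failure under 10.4.4 therefore meets the 8.6 trigger. The meeting rule is affected too: a DSMB first told on day 3 may already have missed the one-business-day limit.

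**Step 3, size of the IRB gap.** 3 days × 24 h = 72 h, and 72 h − 24 h = 48 h. This assumes a common clock start. The sections use different ones: occurrence or recognition (8.6), determination (10.4.4) and the investigator's awareness (8.4.3). The 48 hours is therefore nominal.

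**Step 4, size of the meeting gap.** The longest interval to a quarterly meeting is 365.25 / 4 = 91.3 days, against one business day.

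**Step 5, could the treatment-failure conflict arise?** Take the 98% efficacy in 10.5 and assume independent outcomes. P(at least one failure) = 1 − 0.98^n.
- n = 7 (the 10.5 estimate): 1 − 0.98^7 = 0.132.
- n = 14 (70% of the 20 patients in 5.6): 1 − 0.98^14 = 0.246.

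The documents give no rate for unrelated post-transplant deaths, so no probability is offered for the death conflict.

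**Step 6, do cross-references resolve it?** Only in part. Protocol 8.4.2 and 8.5 point forward to the safety oversight section, and 8.6 points back to 8.4.1 and 8.4.2. But 8.6 does not mention 8.4.3, 10.4.4 or 10.4.7.1, and none of those three mentions 8.5 or 8.6.

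**Two lesser mismatches.**
- Protocol 10.4.4 gives 3 days to report SAEs related to Mavyret or to acute HCV to a *Monitoring committee*, a term also used in 14.3 and not defined in the text provided. Protocol 8.5 requires the IRB and DSMB to be told of the same SAEs within 24 hours. If the term means the DSMB, the DSMB timing differs. Protocol 10.4.4 sets no IRB deadline for these SAEs.
- After a death attributed to an agent, 10.4.7.1 says that patients on that agent are switched. Protocol 8.5 continues treatment unless the DSMB decides otherwise. Protocol 10.4.7.1 names no rival decision-maker, so this is a mismatch of wording.

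**The case against.** The strongest reply is that the rules can be layered.

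- **Death.** Protocol 8.5 does not call its list exhaustive and never says that enrolment continues after an unrelated death. One could pause and assess under 10.4.7.1, then follow 8.5 if the death proves related. A halt is also not termination: 5.8 and 8.5 both provide for review before enrolment continues. This reading is possible, but neither section states it. It leaves the relatedness condition in 8.5 redundant, and 10.4.7.1 gives no restart rule and does not refer to 5.8.
- **Deadlines.** These are outer limits, so a report within 24 hours satisfies every section. That is correct. But 10.4.4 and 8.4.3 allow 3 days without pointing to 8.6, and staff who use that time would miss the shorter limit.
- **Meeting.** The DSMB hears of an unexpected related SAE within 24 hours of its designation, so any deferral would be an informed decision. For SAEs related to Mavyret or acute HCV, 8.5 also calls for an emergency meeting, so a quarter-long wait is unlikely in practice. That limits the practical effect, but the meeting is still mandatory in one section and discretionary in another.
- **DSMB Charter.** Protocol 8.6 refers to it, and it is not among the documents. It may settle some meeting and notification points, but the protocol text would still have to agree with it.

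**Conclusion.** The concern holds. The current protocol contradicts itself on four points: an unrelated death, the IRB deadline for a treatment failure needing rescue, the IRB deadline for a serious related unanticipated problem, and whether an unexpected related SAE requires an emergency meeting. The IRB gap is up to 48 hours if the clocks start together. The meeting gap runs from one business day to at most about 91 days, the upper end being unlikely in practice.

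That the texts differ is certain from reading them. The practical consequence is less certain because the DSMB Charter was not available. The SVR definition and its analysis are unaffected. The conclusion rests on the four main conflicts and does not depend on the two lesser mismatches.

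**What to change.** Reconcile Protocol 8.4.2, 8.4.3, 8.5, 8.6, 10.4.4 and 10.4.7.1 so that each event has one trigger, one deadline with a stated clock start, and one rule on whether an emergency meeting is mandatory. In the same edit:

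- State whether a death not judged related pauses enrolment and how enrolment resumes, with a cross-reference to 5.8.
- Add cross-references from 8.4.3, 10.4.4 and 10.4.7.1 to 8.5 and 8.6.
- Define *Monitoring committee* in 10.4.4 and 14.3, or replace it with DSMB if that is what is meant.
- Reconcile the treatment-switch wording in 10.4.7.1 with the DSMB's role in 8.5.
- Check the result against the DSMB Charter.

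The sponsor and DSMB choose which rule stands in each case; no view is given here. The cost is wording in six subsections, one term in 14.3 and the Charter check. No new data or procedures are needed.
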